6.8.2 Secondary Efficacy Analysis

6.8.2.1 Lesion Counts

The absolute change from Baseline in non-inflammatory lesion count at Day 84 will be summarized similarly as absolute change from Baseline for inflammatory lesion count (primary efficacy endpoint). Percent change from Baseline to Day 84 in inflammatory and non-inflammatory lesion counts will be analyzed using the same ANCOVA method described for the primary endpoint.

6.8.2.2 Investigator Global Assessment

The proportion of subjects with at least a 2-grade reduction from the Baseline IGA score at Day 84 will be analyzed with logistic regression. Pairwise tests will be conducted comparing the treated groups to a combined vehicle. The proportion of subjects with an IGA score of “clear” or “almost clear” at Day 84 will be analyzed using the same logistic method as described above.

The IGA will be dichotomized into “success” and “failure”, with a subject considered a “success” at each individual visit if the IGA at that visit is Clear (“0”) or Almost Clear (“1”) and at least 2 grades less than the Baseline score. The proportion of subjects who are dichotomized to success at Day 84 will be analyzed using the same logistic method as described above.

6.8.3 Exploratory Efficacy Analysis

6.8.3.1 Lesion Counts

The absolute and percent change from Baseline in the total lesion count at Day 84 will be summarized with descriptive statistics.

Additional comparisons between vehicle BID to BTX 1503 BID and vehicle QD to each BTX 1503 QD group for the absolute and percent change from Baseline to Day 84 in inflammatory and non-inflammatory lesion counts will be analyzed using either parametric or non-parametric methods consistent with the approach used for the primary endpoint using an ANCOVA with factors of treatment where no treatment groups are combined and the respective Baseline lesion count as a covariate or on ranked data submitted to an ANCOVA with factors of treatment where no treatment groups are combined and the respective Baseline lesion count as a covariate.

A further comparison will be made between vehicle QD to a combined BTX 1503 QD group for the absolute and percent change from Baseline to Day 84 in inflammatory and non-inflammatory lesion counts using an ANCOVA with factors of treatment where the two BTX 1503 QD treatment groups are combined and the respective Baseline lesion count as a covariate or on ranked data submitted to an ANCOVA with factors of treatment where the two BTX 1503 QD treatment groups are combined and the respective Baseline lesion count as a covariate.

The absolute and percent change from Baseline in inflammatory, non-inflammatory, and total lesion counts will be summarized at Day 14, Day 28, and Day 56. The absolute and percent change from Baseline in inflammatory, non-inflammatory, and total lesion counts at Day 14, Day 28, and Day 56 will be analyzed using the same ANCOVA method used for the primary endpoint as well as the additional testing described above in this section.

6.8.3.2 Investigator Global Assessment

The dichotomized IGA success at Day 84 will be analyzed with an additional logistic regression analysis where no treatment groups are combined. Pairwise tests will be conducted comparing the vehicle BID to BTX 1503 BID and comparing the vehicle QD to each BTX 1503 QD group. The dichotomized IGA success at Day 84 will additionally be analyzed with a logistic regression

where the two BTX 1503 QD treatment groups are combined. Pairwise tests will be conducted comparing the vehicle QD to BTX 1503 QD combined.

The change from Baseline in the IGA scores at Day 14, Day 28, Day 56, and Day 84 will be summarized with descriptive statistics. The proportion of subjects who are dichotomized to success at Day 14, Day 28, and Day 56 will be summarized with proportions. The dichotomized success at Day 14, Day 28, and Day 56 will also be analyzed using the same logistic method as in the secondary efficacy analysis as well as the additional testing described above in this section.

6.8.3.3 Acne-QoL

The change from Baseline in the Acne-QoL domain scores at Day 84 will be summarized with descriptive statistics by domain score and treatment group. Domains for the Acne-QoL include Self-Perception, Role-Social, Role-Emotional, and Acne Symptoms. Responses will be coded numerically on a scale from 0 ('extremely' or 'extensive') to 6 ('not at all' or 'none') within each domain. All questions in each domain will be summed to get the total domain score.

Self-Perception includes Q1, Q2, Q3, Q6, and Q10; Role-Social includes Q11, Q12, Q13, and Q14; Role-Emotional includes Q4, Q5, Q7, Q8, and Q9; and Acne Symptoms includes Q15, Q16, Q17, Q18, and Q19 (Martin 2001).

Domain scores as well as individual question responses will be listed in a by-subject listing.

6.8.3.4 Patient Reported Outcome (PRO)

The PRO will be summarized with counts and percentages by treatment group.

PRO results will also be shown in a by-subject listing.

6.9 Sensitivity Analyses

A sensitivity analysis will be performed using the ITT population. The primary and the first secondary endpoints (change from Baseline in inflammatory and non-inflammatory lesion counts) will be analyzed using a repeated measures ANCOVA, with treatment group and visit as independent factors and the Baseline value as a covariate.

```
proc mixed data = datain method = ML;
  class SUBJECT TRT VISIT;
  model CHG = TRT VISIT TRT * VISIT BASE / solution;
  repeated VISIT / subject = SUBJECT type = cs;
  lsmeans TRT | VISIT / diff;
run;
```

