6. STATISTICAL AND ANALYTICAL PLANS

6.1 General Methodology

All statistical processing will be performed using SAS® 9.3 or higher. No interim analyses are planned. This Phase 2 study is designed to identify the response to two different dosing frequencies and two concentrations of BTX 1503. Statistical tests applied to the outcomes will be exploratory. No adjustments for Type I error will occur.

Descriptive statistics will be used to provide an overview of the efficacy and safety results. For categorical parameters, the number and percentage of subjects in each category will be presented. For continuous parameters, descriptive statistics will include n (number of subjects), mean, standard deviation (SD), median, minimum and maximum.

The primary method of handling missing efficacy data in the ITT analysis set will be based on last observation carried forward (LOCF). Repeated measures analyses will be used on the observed data as a sensitivity analysis on the primary endpoint and the first secondary endpoint.

The efficacy analysis performed on the ITT population is considered the primary analysis. The efficacy analysis performed on the per-protocol (PP) population is considered supportive analysis.

The number of subjects in each analysis set will be summarized. Reasons for study withdrawal during the study will be summarized using frequencies and percentages by treatment group.

Reported AEs, medical history terms, and prior and concomitant procedures and therapies will be classified on the basis of Medical Dictionary for Regulatory Activities (MedDRA) terminology. Prior and concomitant medications will be classified on the basis of World Health Organization Drug Dictionary (WHO-DDE) terminology.

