6.1.4 Adjustments for Covariates

Baseline lesion count will be a covariate for the efficacy endpoints for acne lesion counts. No other covariates are planned to be used in the analyses for this study.

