6.8.1 Primary Efficacy Analysis

Absolute change from Baseline to Day 84 in inflammatory lesion counts will be analyzed using either parametric or non-parametric methods consistent with the statistical assumptions required to support the analyses. Specifically, the tests of superiority will be based on an ANCOVA with factors of treatment (with the vehicle treatment groups combined) and the respective Baseline lesion count as a covariate, or on ranked data submitted to an ANCOVA with factors of treatment and the respective Baseline lesion count as a covariate.

A skewness test, based on the methods presented by J.H. Zar (1984), will be applied to the residuals resulting from an ANCOVA. A two-sided p-value for the skewness test significant at 0.01 will imply the use of the non-parametric method. If a parametric analysis is indicated, the results of the parametric analysis will be considered the primary analysis. Should a non-parametric analysis be indicated, the absolute changes in inflammatory lesions will be rank transformed prior to submitting them to the ANCOVA. Results of the rank-transformed analyses then will be considered the primary analysis; however, results of the non-ranked transformed analyses will also be presented.

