SD	xx.xx	xx.xx	xx.xx	xx.xx	xx.xx	xx.xx	
Median	xx.x	xx.x	xx.x	xx.x	xx.x	xx.x	
Min., Max.	xx, xx	xx, xx	xx, xx	xx, xx	xx, xx	xx, xx	
LSMean ^a			xx.x	xx.x	xx.x	xx.x	0.xxxx ^b
LSSD ^a			xx.xx	xx.xx	xx.xx	xx.xx	
Unranked P-value vs. Combined Vehicle ^a				0.xxxx	0.xxxx	0.xxxx	
Ranked P-value vs. Combined Vehicle ^c				0.xxxx	0.xxxx	0.xxxx	

^a Least squares mean, standard deviation, and contrast p-values from an analysis of covariance with factors of treatment group (vehicle treatment groups included as single combined treatment group) and corresponding baseline lesion count as the covariate.

^b Skewness test is based on methods presented by J.H. Zar (1984).

^c Contrast p-values from a ranked analysis of covariance with factors of treatment group (vehicle treatment groups included as single combined treatment group) and corresponding baseline lesion count as the covariate.

Note: Missing values imputed using LOCF.

SOURCE: USERNAME\SPONSOR\PROJECT\JOBNAME (DATE,TIME)

Repeat Table 14.2.1.1 for the following:

Table 14.2.1.2: Primary Efficacy Endpoint: Summary of Absolute Change from Baseline in Inflammatory Lesion Count at Day 84 (PP Population)

Programming note: replace last footnote with:

Note: No imputations were made for missing data.

Table 14.2.1.3: Sensitivity Analysis of Primary Efficacy Endpoint: Summary of Absolute Change from Baseline in Inflammatory Lesion Count at Day 84 (ITT Population)

Repeated Measures Analysis on Observed Data	Vehicle QD (N=xx)	Vehicle BID (N=xx)	Vehicle Combined (N=xx)	BTX 1503 5% BID (N=xx)	BTX 1503 5% QD (N=xx)	BTX 1503 2.5% QD (N=xx)
Change from Baseline in Inflammatory Lesion Counts						
n	xx	xx	xx	xx	xx	xx
Mean	xx.x	xx.x	xx.x	xx.x	xx.x	xx.x
SD	xx.xx	xx.xx	xx.xx	xx.xx	xx.xx	xx.xx
Median	xx.x	xx.x	xx.x	xx.x	xx.x	xx.x
Min., Max.	xx, xx	xx, xx	xx, xx	xx, xx	xx, xx	xx, xx
LSMean ^a			xx.x	xx.x	xx.x	xx.x
LSSD ^a			xx.xx	xx.xx	xx.xx	xx.xx
P-value vs. Combined Vehicle ^a				0.xxxx	0.xxxx	0.xxxx

^a Least squares mean, standard deviation, and contrast p-values from a repeated measures analysis of covariance with factors of treatment group (vehicle treatment groups included as single combined treatment group), visit, treatment by visit interaction, and corresponding baseline lesion count as the covariate. Note: No imputations were made for missing data.

SOURCE: USERNAME\SPONSOR\PROJECT\JOBNAME (DATE,TIME)

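### The LOCF sensitivity model pools one variance over four visits, so its Day 84 p-value can differ from the unranked ANCOVA even with no missing data

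*SAP*

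**What the plan says.** SAP 6.1 states the role of the model: "Repeated measures analyses will be used on the observed data as a sensitivity analysis on the primary endpoint and the first secondary endpoint". SAP 6.9 gives its code. Estimation is by maximum likelihood ("proc mixed data = datain method = ML"), the mean model has one baseline slope for all visits ("model CHG = TRT VISIT TRT * VISIT BASE / solution"), and the covariance line is "repeated VISIT / subject = SUBJECT type = cs". No heterogeneous, unstructured or empirical alternative is named, and the choice is not justified.

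The analysis being checked is in SAP 6.8.1: Day 84 change with LOCF, by "ANCOVA with factors of treatment (with the vehicle treatment groups combined) and the respective Baseline lesion count as a covariate". If the skewness rule selects ranks, SAP 6.8.1 says "Results of the rank-transformed analyses then will be considered the primary analysis; however, results of the non-ranked transformed analyses will also be presented", so an unranked Day 84 result appears in Table 14.2.1.1 in either case.

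The shell of the sensitivity Table 14.2.1.3 reports "Least squares mean, standard deviation, and contrast p-values from a repeated measures analysis of covariance with factors of treatment group", with p-values against combined vehicle. Protocol 9.4.9 names MMRM only as an example of a possible sensitivity analysis and fixes no covariance structure.

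**The concern.** The model is there to show whether the LOCF result depends on how missing values are handled. For that, it should agree with the Day 84 ANCOVA when nothing is missing. With `type=cs` it does so only if the average of the four visit variances happens to equal the Day 84 variance. Otherwise its Day 84 SE is too small (Day 84 more variable than average) or too large (less variable), and its p-value moves with it.

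A gap between the two p-values then cannot be put down to missing data, and agreement could be a coincidence. This is the only ITT check on LOCF for the primary and the first secondary endpoint.

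**Working it through.** **Inputs from the documents.** Four post-baseline visits (Days 14, 28, 56, 84); 90 subjects per active arm and 45 + 45 = 90 on combined vehicle (SAP 7); model and covariance as in SAP 6.9. The sample size rests on clinical considerations only, so there is no SD, effect size or power figure to reproduce.

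**Assumed.** The visit SDs (residual SDs of change, shown as a range), and a two-sided 5% level for illustration.

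**Formula.** With balanced complete data, the fitted compound-symmetry variance equals the mean of the four visit residual variances (numerical agreement to 1e-13). Hence

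- r = SE(CS) / SE(Day 84 ANCOVA) = √(mean visit variance / Day 84 variance)
- rejection rate of a nominal 5% test = 2 × (1 − Φ(1.96 r))
- an ANCOVA p of 0.050 becomes 2 × (1 − Φ(1.96 / r))

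Example, SDs 8, 9, 10, 11: mean variance (64 + 81 + 100 + 121)/4 = 91.5; Day 84 variance 121; r = √(91.5/121) = 0.87. Rejection is 2 × (1 − Φ(1.704)) = 8.8%, and 0.050 becomes 2 × (1 − Φ(2.254)) = 0.024.

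| Assumed SDs, Days 14/28/56/84 | Mean variance | Day 84 variance | r | Rejection | ANCOVA p of 0.050 becomes |
|---|---|---|---|---|---|
| 6, 8, 10, 12 | 86.0 | 144 | 0.77 | 13.0% | 0.011 |
| 8, 9, 10, 11 | 91.5 | 121 | 0.87 | 8.8% | 0.024 |
| 9, 10, 10, 10 | 95.25 | 100 | 0.98 | 5.6% | 0.045 |
| 10, 10, 10, 10 | 100 | 100 | 1.00 | 5.0% | 0.050 |
| 8, 12, 10, 10.13 | 102.7 | 102.6 | 1.00 | 5.0% | 0.050 |
| 10, 11, 11, 10 | 110.5 | 100 | 1.05 | 3.9% | 0.062 |
| 12, 11, 10, 9 | 111.5 | 81 | 1.17 | 2.1% | 0.095 |

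The fifth row shows that unequal variances can cancel.

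**Simulation check.** Complete data, four arms of 90, correlation 0.7 per visit step, baseline SD 8, equal baseline slopes, 40,000 trials per case. The SAP model (CS, ML) rejected 9.2% (8, 9, 10, 11), 5.1% (flat) and 2.2% (12, 11, 10, 9); the Day 84 ANCOVA rejected 4.9 to 5.1%. In a single simulated trial with SDs 6, 7.5, 9, 10 and correlation 0.6, the CS model gave SE 1.209 at every visit, while separate ANCOVAs gave 0.890, 1.095, 1.423 and 1.382.

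**With dropout.** With 12% random monotone dropout and ML, the rates are 9.6% (8, 9, 10, 11), 5.5% (flat) and 2.4% (12, 11, 10, 9).

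**Two smaller effects of the same code.**

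- ML instead of REML lowers the SE by about 0.65%.
- The single baseline slope can shift the Day 84 estimate. For SDs 8, 9, 10, 11 the SE of the difference is about 11 × √(2/90) = 1.64 lesions. Against that, the mean shift is 0.03 lesions with equal slopes. It is 0.14 if true slopes run from −0.15 to −0.45 over the visits, and 0.28 if they run from −0.1 to −0.7.

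**The case against.** The algebra is not in dispute. The case against giving it weight is this.

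- **No defect is shown for this trial.** Every SD above is assumed, and the range runs from inflation through no effect to conservatism. That is true and stays as a limit on the finding. The point is that the model's validity rests on an equality that the SAP neither argues for nor tests.
- **Little hangs on the p-value.** The tests are exploratory, there is no Type I error control, and no decision rule reads this result. That also stands, and it keeps the point at the level of a recommended change.
- **The estimate is sound.** Under 12% random dropout (SDs 8, 9, 10, 11) the true SE of the CS estimate is 1.723 against 1.717 for an unstructured fit, and the shifts in the estimate are small. So comparing LSMeans between Tables 14.2.1.1 and 14.2.1.3 still says something about LOCF. This stands: only the SE and p-value are exposed, but the p-value is what the shell uses for the comparison with vehicle.
- **The planned tables already reveal the problem.** The sensitivity table prints the observed Day 84 SD beside the model LSSD. If LSSD is a residual SD, which the SAP does not define, their ratio in simulation was 0.85, 0.97 and 1.13 with 12% random dropout, against true values of 0.87, 1.00 and 1.17 (rising, flat, falling). With 27–29% outcome-related dropout it was 0.88, 1.01 and 1.18. The unimputed PP ANCOVA (Table 14.2.1.2) is also free of pooling, but in a different population. A careful reader could therefore suspect the fault; none of this corrects the reported p-value.
- **The remedy is wider than the fault.** An unstructured covariance alone removes the main effect. REML and the baseline-by-visit term deal with the two smaller effects and are needed for an exact match to the ANCOVA. Confidence intervals are good practice rather than a correction.

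**Conclusion.** The concern holds. With complete data, the SAP 6.9 model gives a Day 84 SE that differs from the unranked ANCOVA's by √(mean visit variance / Day 84 variance), apart from the small ML and slope effects. For the assumed profiles that factor runs from 0.77 to 1.17, and a nominal 5% test rejects between 13.0% and 2.1% of the time. It is harmless if the mean and Day 84 variances match. Size and direction cannot be stated for this trial, because the documents give no visit SDs.

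The consequence is limited to interpretation: the only ITT check on LOCF cannot separate missing-data handling from variance pooling. The primary LOCF ANCOVA is unaffected, and the exploratory status keeps the stakes modest. The change is worth making because it is cheap.

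**What to change.** Before unblinding, replace the SAP 6.9 code with:

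- `method=REML`
- `model CHG = TRT VISIT TRT*VISIT BASE BASE*VISIT / ddfm=kr`
- `repeated VISIT / subject=SUBJECT type=un`

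Pre-specify a fallback for non-convergence (heterogeneous Toeplitz, then heterogeneous compound symmetry) and report which structure was used. Add Day 84 differences from combined vehicle with 95% CIs to the two sensitivity shells. State that the comparison is with the unranked LOCF ANCOVA, since a rank-based primary result is on another scale.

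The adjustment set stays that of the primary model; SAP 6.1.4 says "No other covariates are planned to be used in the analyses for this study", and the added term only lets the same baseline slope vary by visit. Whether site belongs in both models is a separate question.

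On one complete simulated trial the new code gave the ANCOVA's estimate and SE (1.978 and 1.615) to at least 10 decimals. A remaining difference from the unranked LOCF ANCOVA would then reflect missing-data handling; under a fallback structure this holds only approximately.

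The cost is a few words of code and one CI row in two shells. The model has 10 covariance parameters instead of 2, and 3 more slopes, for about 360 subjects. The small risk of non-convergence is covered by the fallback. Protocol 9.4.9 fixes no covariance structure, so no amendment is needed, and patients and data collection are not affected.

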6.10 Safety Evaluation

6.10.1 Extent of Exposure

The extent of exposure to study drug in each treatment group will be summarized by total number of days of exposure, total number of applications, number of missed applications, number and percentage of subjects who are compliant, average amount of study drug used per day (g/day), and amount of drug used total (g). A subject will be considered compliant with the dosing regimen if the subject applied 80% to 120% of the expected number of applications while enrolled in the study.

The total amount of study drug used will be calculated from the drug accountability using the recorded weights. The difference between the dispensed weight and the returned weight for each pump will be summed over all pumps to get the total amount of study drug used. The total amount of study drug used will be divided by the total number of exposure days to get the average amount of study drug used per day.

The total number of days of exposure is as follows:

$$\text{Date of Last Application} - \text{Date of First Application} + 1.$$

It will be assumed the BID subjects were expected to have 2 applications on the Date of First Application. It will also be assumed the BID subjects were expected to have only 1 application on the Date of Last Application unless there is evidence to suggest otherwise (i.e. dosing deviation log indicates 2 doses were expected).

The total number of applications taken for BID subjects is as follows:

$$2 \text{ applications expected on Date of Last Application: } 2 * (\text{Date of Last Application} - \text{Date of First Application} + 1) - (\text{Number of doses marked as missed on the CRF});$$

$$1 \text{ application expected on Date of Last Application: } 2 * (\text{Date of Last Application} - \text{Date of First}) + 1 - (\text{Number of doses marked as missed on the CRF}).$$

The total number of applications taken for QD subjects is as follows:

$$(\text{Date of Last Application} - \text{Date of First Application} + 1) - (\text{Number of doses marked as missed on the CRF}).$$

The total number of applications expected for BID subjects is as follows:

$$2 \text{ applications expected on Date of Last Application: } 2 * (\text{Date Subject Ended Participation} - \text{Date of Randomization} + 1);$$

1 application expected on Date of Last Application: $2 * (\text{Date Subject Ended Participation} - \text{Date of Randomization}) + 1$.

The total number of applications expected for QD subjects is as follows:

$\text{Date Subject Ended Participation} - \text{Date of Randomization} + 1$.

If the total number of applications for BID subjects exceeds 178 then it will be set to 178.

If the total number of applications for QD subjects exceeds 89 then it will be set to 89.

Compliance will be calculated as a percentage as 100 times the total number of applications taken divided by the total number of applications expected while enrolled in the study.

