7.3.8. Schedule of Events Table – Subjects with Acne Vulgaris

The Schedule of Events is provided in [Table 3](#).

Table 3: Time and Events Schedule

| Parameter | Screening Visit (-35 to Day 1) | Baseline Visit (Day 1)^a | Day 14 Visit (Day 14 ±3 days) | Day 28 Visit (Day 28 ±5 days) | Day 56 Visit (Day 56 ±5 days) | Day 84 Visit^c (Day 84 ±5 days) |
|---------------------------------------------------|-------------------------------------------|----------------------------------------------------------------------------------|------------------------------------------|------------------------------------------|------------------------------------------|------------------------------------------------------|
| | Visit 1 | Visit 2 | Visit 3 | Visit 4 | Visit 5 | Visit 6 |
| Written informed consent/assent | X | | | | | |
| Medical history/ review of systems | X | | | | | |
| Demographics with Height and Weight | X | | | | | |
| Tobacco and Alcohol History | X | | | | | |
| Urine pregnancy test (WOCBP only) | X | X | | X | X | X |
| Eligibility criteria review | X | X | | | | |
| Safety Laboratory (CBC, chemistry and urinalysis) | | X | | | | X |
| Urine drug screening | X | X | | | | |
| Investigator's Global Assessment | X | X | X | X | X | X |
| Inflammatory and non-inflammatory lesion count | X | X | X | X | X | X |
| Photography of Face (selected sites) | | X | | | | X |
| Administer Acne-QoL | | X | | | | X |
| Administer PRO | | | | | | X |
| Ensure compliance with study drug administration | | | X | X | X | X |
| Study drug administration by site personnel (am) | | X | | | | |
| Study drug administration by subject | | Day 1 pm to Day 84 ^d ; Day 14, 28, 56, and 84 doses applied in clinic | | | | |
| Concomitant medications | X | X | X | X | X | X |
| Adverse events | | X | X | X | X | X |
| Cutaneous tolerability assessments ^b | | X | X | X | X | X |
| Dispense study drug and diary | | X | | X | X | |
| Collect diary and study drug | | | | X | X | X |

^a Screening and Baseline Visit may occur on the same day.

^b Assess cutaneous tolerability prior to and approximately 15 min after initial dose on Day 1 and the subject applications on Day 14, Day 28, Day 56, and Day 84

^c If subject discontinues treatment early, Day 84 evaluations will be performed when possible.

^d Subjects randomized to BID dosing will apply study drug in the morning and evening, 8 to 12 hours apart.

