6.4.4 Per-Protocol (PP) Population

All subjects in the ITT population who complete the Day 84 visit without noteworthy study protocol violations will be included in the PP population and analyzed according to the treatment group received. The PP population will include subjects in the ITT population who do not meet any of the following criteria:

- Violated the inclusion/exclusion criteria;
- Have taken any interfering concomitant medication;
- Did not complete both IGA and lesion count efficacy assessments at the Day 84 visit;
- Have missed both the Day 28 and Day 56 visits;
- Have not been compliant with the dosing regimen (i.e. subjects must apply 80-120% of the expected applications of study medication during participation in the study);
- Out of visit window at the Day 84 visit by ± 5 days;

Subjects that discontinue from the study due to an AE related to study treatment or documented lack of treatment effect will be included in the PP population. Prior to breaking the blind, other

additional criteria may be added to the list to accommodate for unforeseen events that occurred during the conduct of the trial that result in noteworthy study protocol violations.

All efficacy analyses will be performed on the PP population.

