xxxxxxx	xxxx	xxxxxxxxxx	xxxxxxxxxx xxx xx xxx xx xxx xx	xxxx-xx-xxTxx:xx:xx xxxx-xx-xxTxx:xx:xx xxxx-xx-xxTxx:xx:xx xxxx-xx-xxTxx:xx:xx	xxxxxx xxxxxx xxxxxx xxx xxxxxxxxxxxx	xx xxxxx xxxxxxxxxxxx
xxxxxxx	xxxx	xxxxxxxxxx	xxxxxxxxxx xxx xx xxx xx xxx xx	xxxx-xx-xxTxx:xx:xx xxxx-xx-xxTxx:xx:xx xxxx-xx-xxTxx:xx:xx xxxx-xx-xxTxx:xx:xx	xxxxxx xxxxxx xxxxxx xxxxxx	

SOURCE: USERNAME\SPONSOR\PROJECT\JOBNAME (DATE, TIME)

Listing sorted by Subject, visit, Date/Time.

Listing 16.2.5.3: Drug Accountability
 Treatment Group
 (Page xx of yy)

Subject	Age/Sex	Evaluable	Kit Number	Date Dispensed	Date Returned	Pump ID	Dispensed Weight (units)	Returned Weight (units)
xxxxxx	xxxx	xxxxxxxxx	xxxxx	xxxx-xx-xx	xxxx-xx-xx	x	xx.xx	xx.xx
						x	xx.xx	xx.xx
						x	xx.xx	xx.xx
						x	xx.xx	xx.xx
			xxxxx	xxxx-xx-xx	xxxx-xx-xx	x	xx.xx	xx.xx
						x	xx.xx	xx.xx
						x	xx.xx	xx.xx
						x	xx.xx	xx.xx
			xxxxx	xxxx-xx-xx	xxxx-xx-xx	x	xx.xx	xx.xx
						x	xx.xx	xx.xx
						x	xx.xx	xx.xx
						x	xx.xx	xx.xx
						x	xx.xx	xx.xx
						x	xx.xx	xx.xx
xxxxxx	xxxx	xxxxxxxxx	xxxxx	xxxx-xx-xx	xxxx-xx-xx	x	xx.xx	xx.xx
						x	xx.xx	xx.xx
						x	xx.xx	xx.xx
						x	xx.xx	xx.xx
			xxxxx	xxxx-xx-xx	xxxx-xx-xx	x	xx.xx	xx.xx
						x	xx.xx	xx.xx
						x	xx.xx	xx.xx
						x	xx.xx	xx.xx

SOURCE: USERNAME\SPONSOR\PROJECT\JOBNAME (DATE, TIME)

Listing sorted by Subject, Kit Number, Date Dispensed, Date Returned.

Listing 16.2.5.4: Dosing Compliance
 Treatment Group
 (Page xx of yy)

S: Subject	D: Date of First Dose	Number of Days of Exposure	Calculated ¹ Number of Doses	Amount of Study Drug Used (g)	Number of Missed Doses	Percent Complaint	Compliant? ²
A: Age/Sex E: Evaluable S: xxxxxx D: xxxx-xx-xx R: xxxx-xx-xx xx xx xxxx xxx xxx							
S: xxxxxx D: xxxx-xx-xx R: xxxx-xx-xx xx xx xxxx x xxx xx							
S: xxxxxx D: xxxx-xx-xx R: xxxx-xx-xx xx xx xxxx xxxx xxx							

¹ The total number of doses was calculated from the date of first dose and the date of last known dose minus the missed doses.

² A subject was considered compliant with the dosing regimen if the subject applied at least 80% but no more than 120% of the expected applications.

SOURCE: USERNAME\SPONSOR\PROJECT\JOBNAME (DATE, TIME)

Listing 16.2.5.5: Dosing Deviations
 Treatment Group
 (Page xx of yy)

Subject	Age/Sex	Evaluable	Date (Day) ¹ of Missed Dose	Morning or Afternoon dose?	Reason for Missed Dose
xxxxxx	xxxx	xxxxxxxx	xxxx-xx-xx (xx) xxxx-xx-xx (xx) xxxx-xx-xx (xx)	xx xx xx	xxxxx xxxxxxxxxxx xxxxxxxx xxxxxxxx xxxxxxx xx

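### If sites log doses after the last application as missed, the SAP's compliance formula removes those doses twice

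*SAP*

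**What the plan says.** SAP 6.10.1 derives applications taken from dates. For QD it is the inclusive day count from first to last application, less the "Number of doses marked as missed on the CRF". For BID the span is counted at two applications a day, with one or two on the last date according to what was expected then, and the same missed-dose term is subtracted. Footnote 1 to Listing 16.2.5.4 repeats the rule: "The total number of doses was calculated from the date of first dose and the date of last known dose minus the missed doses". Neither place limits the missed doses by date.

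Applications expected run over a different interval, from randomisation to the end of participation. Compliance is taken over expected, as a percentage. There is an upper cap ("If the total number of applications for QD subjects exceeds 89 then it will be set to 89"; 178 for BID) but no lower bound.

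The percentage decides PP membership. Under SAP 6.4.4, "subjects must apply 80-120% of the expected applications of study medication during participation in the study". The same section keeps in the PP set anyone who discontinues for a treatment-related AE or documented lack of effect.

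The protocol foresees visits after drug has stopped. Footnote c to Table 3 in Section 7.3.8 reads: "If subject discontinues treatment early, Day 84 evaluations will be performed when possible".

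**The concern.** The numerator stops at the last application and the denominator runs on to the end of participation. An early stop therefore lowers compliance once already, as it should. A missed-dose entry dated after the last application was never in the numerator's span, so subtracting it charges the same dose again.

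Such entries are foreseeable. Listing 16.2.5.5 holds a date for each missed dose with no stated cut-off. Listing 16.2.5.1 has a column for why drug was not administered at a visit. Listing 16.2.7.2.4 treats stopping drug and leaving the study as separable events.

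Three outputs are exposed:
- PP membership, through the 80% limit.
- The application count and compliance rows of Table 14.3.0.1 (safety population).
- The split at median compliance in the responder summaries (SAP 6.1.11.1).

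**Working it through.** **Inputs.** Formulas, caps and the 80% limit come from SAP 6.10.1. Planned doses (QD 84, BID 167) come from Protocol 6.1.8. Assumptions: randomisation and first application on Day 1; last application on Day L; no misses up to then; participation ends on Day 84; every dose due after the last application is logged as missed.

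**The plan's own figures.** For a completer, QD is 84 - 1 + 1 = 84 and BID is 2 × (84 - 1) + 1 = 167. Both match Protocol 6.1.8. The caps match the latest visit day, 84 + 5 = 89: QD 89, BID 2 × 89 = 178. The formulas are sound when the last application falls on the final day.

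**QD.** True applications = L. Later doses logged = 84 - L. The rule gives L - (84 - L) = 2L - 84. Expected = 84.

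| Last application | Days before end | True | Rule |
|---|---|---|---|
| Day 76 | 8 | 76/84 = 90.5% | 68/84 = 81.0% |
| Day 75 | 9 | 75/84 = 89.3% | 66/84 = 78.6% |
| Day 68 | 16 | 68/84 = 81.0% | 52/84 = 61.9% |
| Day 67 | 17 | 67/84 = 79.8% | 50/84 = 59.5% |
| Day 40 | 44 | 40/84 = 47.6% | -4/84 = -4.8% |
| Day 30 | 54 | 30/84 = 35.7% | -24/84 = -28.6% |

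The status is wrong for a last application on Days 68 to 75. The count is below zero when 2L < 84, that is, up to Day 41.

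**BID.** Doses due after Day L are 2 × (83 - L) + 1 = 167 - 2L. The SAP pairs two applications on the last date with 2 × 84 = 168 expected, and one with 167.

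| Last application | Two on last date: true | Rule | One on last date: true | Rule |
|---|---|---|---|---|
| Day 76 | 152/168 = 90.5% | (152 - 15)/168 = 81.5% | 151/167 = 90.4% | (151 - 15)/167 = 81.4% |
| Day 75 | 150/168 = 89.3% | (150 - 17)/168 = 79.2% | 149/167 = 89.2% | (149 - 17)/167 = 79.0% |
| Day 68 | 136/168 = 81.0% | (136 - 31)/168 = 62.5% | 135/167 = 80.8% | (135 - 31)/167 = 62.3% |
| Day 67 | 134/168 = 79.8% | already below 80% | 133/167 = 79.6% | already below 80% |

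The window is again 9 to 16 days before the end. The count is 4L - 167 or 4L - 168, negative up to Day 41 in both cases.

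**Other end days (QD).** With participation to Day 79 the window is Days 64 to 71, and the count is negative up to Day 39. With participation to Day 89 it is Days 72 to 80, negative up to Day 44.

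**Other logging convention.** If no dose after the last application is logged as missed, nothing is subtracted. The QD rule then returns L, the true count, for every L.

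**The case against.** The strongest defence is that the formula is right if missed is understood as missed during the dosing span. The numerator then nets off gaps inside the span and the denominator carries the untreated tail. SAP 6.10.1 consults the dosing deviation log to decide whether one or two BID doses were due on the last date, which suggests that span and log were meant to agree. The CRF completion rules are not among the documents, and dated entries in a listing do not show that entries continue after drug stops. This stands, and it makes the point conditional. It does not remove the point: the written formula has no such limit, and its result should not depend on how sites fill in a log.

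The exposed group is also narrow. The final dose is applied in clinic at Day 84, so a subject who lapses but applies that dose has no gap. Protocol 5.3.1 ends enrolment and drug together at withdrawal, and later evaluations are only sought when possible. Related-AE and lack-of-effect discontinuers stay in the PP set. All of this stands.

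Finally, Listing 16.2.5.4 would show a negative count, and evaluability is settled before unblinding. That protects against the gross cases. It would not flag a QD subject with 75 days of exposure, 9 missed doses and 66 calculated doses, who looks like someone with 9 gaps during treatment.

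**Conclusion.** The point holds in conditional form and is minor. If doses after the last application are logged as missed, with no earlier misses and participation to Day 84, QD and BID subjects whose last application is 9 to 16 days before the end are wrongly non-compliant. Those with an otherwise valid Day 84 assessment would drop out of the supportive PP set unless the 6.4.4 exception covers them. The application count in Table 14.3.0.1 is understated for any such stopper. The number of such subjects cannot be derived from the documents. Subjects whose last application is on their final day are unaffected.

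The documents do not support four stronger inferences that a reader might draw:
- **That the double removal will occur.** It depends on a logging convention that neither document states.
- **That negative counts distort PP membership.** A QD subject who stops by Day 41 is at most 41/84 = 48.8% compliant and fails the 80% limit under any rule. Only the exposure summary is affected.
- **That the BID window reaches 17 days.** That needs two doses on the last date over 167 expected (134/167 = 80.2%). The SAP's own pairings give 79.8% and 79.6% before anything is subtracted.
- **That the main efficacy result is at risk.** The primary analysis is ITT, and PP is supportive.

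**What to change.** In SAP 6.10.1, in the QD formula and both BID formulas, and in footnote 1 of Listing 16.2.5.4, restrict the subtracted term to missed doses dated from the first through the last application. Leave the missed-applications row of Table 14.3.0.1 as the full count. An evening BID dose missed on the last application date stays inside the filter, which agrees with the SAP's allowance of two expected doses on that date.

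This gives the correct count whether or not sites log doses after the stop. Defining taken as expected minus all missed would be less safe, because it is right only if every later dose is logged.

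The cost is one phrase and one date filter in the program. The missed-dose date is already collected, so no new data are needed. The change should be made before PP membership is decided.
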